1.6. Potential benefits and risks of Intervention

Although it can be hypothesised that antifibrinolytics may decrease the risk of severe and life-threatening bleeding and decrease patients' exposure to blood components, these drugs also have the potential to increase the rate of thromboembolism. Patients with an underlying malignancy have a higher rate of thromboembolic disease. In a retrospective cohort study of thromboembolism in hospitalised neutropenic cancer patients, 4% (593/14,600) of acute leukaemia patients developed venous thromboembolism (VTE) and 1.9% (279/14,600) of patients with acute leukaemia developed arterial thromboembolism (31). A meta-analysis of 29 different cohorts of patients with lymphoma gave an estimate of 6.4% (95% confidence interval 6.1 to 6.9%) (32). The one year incidence of symptomatic VTE in patients undergoing stem cell transplantation has been estimated at 3.7% (33). The most common type of venous thromboembolism in this group of patients is line associated thrombosis with an estimated incidence of 2.6 to 5% (33, 34).

1.7. Specific objectives or hypotheses

The hypothesis is that in patients with haematological malignancies, during a period of severe thrombocytopenia, prophylactic use of antifibrinolytics would decrease bleeding and the demand for platelet transfusions. There may also be additional benefits for patients such as improved quality of life during their in-patient stay and earlier discharge home. Given the importance of understanding the cost-effectiveness of new treatments, this trial proposal will also incorporate a health economic analysis.

1.8. Description of trial design

This is a double-blind, placebo controlled parallel group trial to assess the safety and efficacy of tranexamic acid at reducing bleeding in patients with haematological malignancies and severe thrombocytopenia. Participants will be randomised to receive TXA or placebo.

2. Trial Setting

This trial will be conducted in the haematology wards of participating hospitals in the UK and Australia.

3. Selection of Sites/Clinicians

Centre selection in UK will be based on the presence of appropriate clinical and research infrastructure including adequate local resources and facilities to support recruitment, and adequate qualified staff to conduct the trial properly and safely. Therefore recruiting centres

will be drawn from those involved in TOPPS (20) who have experience of conducting platelet studies..

The trial management group (TMG) will invite eligible centres and will discuss the resources required for conducting the trial, including the importance of delivering training and education to the clinical staff on the use of the bleeding assessment tool.

All UK local laboratories should be Clinical Pathology Accreditation accredited, and National External Quality Assurance Scheme participants. Australian centres will be NATA/RCPA accredited.

3.1. Site/Investigator Inclusion Criteria

To participate in the TREATT trial, investigators and clinical trial sites must fulfil a set of basic criteria that have been prepared by the TREATT Trial Management Group (TMG) and are defined below.

PI Qualifications and Agreements

The investigator should be qualified by education, training and experience to assume responsibility for the proper conduct of the trial at their site and should provide evidence of such qualifications through an up to date curriculum vitae and/or other relevant documentation requested by the Sponsor, the REC, and/or the regulatory authorities.

3.2. Site/Investigator Exclusion Criteria

The General Medical Council's List of Registered Medical Practitioners, or the Australian Health Practitioner Regulation Agency, will be consulted to ensure all potential PIs are licensed to practice. Any PI without a current licence or with a history of non-fitness to practice should not be approached.

3.3. Recruitment

The site selection process will include a rigorous evaluation of the site's potential rate of accrual to the trial, which will include a review of types of patient treated, an assessment of how many would be eligible, and how many may be recruited given the site level resource and any barriers to recruitment such as other trials competing to recruit the same patient population.

4. Selection of Participants

There will be no exceptions to eligibility requirements at the time of randomisation. Participants will be considered eligible for enrolment in this trial if they fulfil all the inclusion criteria and none of the exclusion criteria detailed below.

4.1. Participant Inclusion Criteria

Patients are eligible for this trial if:

1. Aged ≥ 18 years of age
2. Confirmed diagnosis of a haematological malignancy
3. Undergoing chemotherapy, or chemotherapy is planned, or haematopoietic stem cell transplantation
4. Anticipated to have a hypoproliferative thrombocytopenia resulting in a platelet count of $\leq 10 \times 10^9/L$ for ≥ 5 days
5. Able to comply with treatment and monitoring

4.2. Participant Exclusion Criteria

A patient will not be eligible for this trial if he/she fulfils one or more of the following criteria:

1. Patients with a past history or current diagnosis of arterial or venous thromboembolic disease including myocardial infarction, peripheral vascular disease and retinal arterial or venous thrombosis.
2. Diagnosis of acute promyelocytic leukaemia (APML) and undergoing induction chemotherapy
3. Patients with a diagnosis/previous history of veno-occlusive disease (also called sinusoidal obstruction syndrome)
4. Patients with known inherited or acquired prothrombotic disorders e.g.
 - a. Lupus anticoagulant
 - b. Positive antiphospholipids
5. Patients receiving any pro-coagulant agents (e.g. DDAVP, recombinant Factor VIIa or Prothrombin Complex Concentrates (PCC) within 48 hours of enrolment, or with known hypercoagulable state
6. Patients receiving L-asparaginase as part of their current cycle of treatment
7. History of immune thrombocytopenia (ITP), thrombotic thrombocytopenic purpura (TTP) or haemolytic uraemic syndrome (HUS)
8. Patients with overt DIC (See Appendix 3 in the protocol for definition)
9. Patients requiring a platelet transfusion threshold $>10 \times 10^9/L$ at time of randomisation. (This refers to patients who require their platelet count to be maintained at a certain specified level on an ongoing basis, and excludes a transient rise in the threshold due to sepsis.)
10. Patients with a known inherited or acquired bleeding disorder e.g.
 - a. Acquired storage pool deficiency
 - b. Paraproteinaemia with platelet inhibition
11. Patients receiving anticoagulant therapy or anti-platelet therapy
12. Patients with visible haematuria at time of randomisation
13. Patients with anuria (defined as urine output < 10 mls/hr over 24 hours).
14. Patients with severe renal impairment ($eGFR \leq 30$ ml/min/1.73m²)
15. Patients with a previous history of epilepsy, convulsions, fits or seizures
16. Patients who are pregnant or breast-feeding
17. Allergic to tranexamic acid.
18. Patients enrolled in other trials involving platelet transfusions, anti-fibrinolytics, platelet growth factors or other pro-coagulant agents.
19. Patients previously randomised into this trial at any stage of their treatment.

4.3. Co-Enrolment Guidelines

Please refer to Section 5.7

4.4. Screening/Recruitment

A screening log will be completed on all patients admitted to the participating units with a haematological malignancy and undergoing chemotherapy or a stem cell transplant who are expected to develop a hypoproliferative thrombocytopenia resulting in a platelet count of $\leq 10 \times 10^9/L$ for ≥ 5 days. The log will include main diagnosis and treatment plan. It will include

patients approached but in whom consent was not obtained for the trial (with reasons) and therefore will define how representative randomised patients are as a group relative to the group of eligible patients who were not randomised.

The local PI or delegate will be responsible for identifying suitable patients and inviting them to participate in the trial.

Each participant will be assigned a unique trial number consisting of 6 digits, the first 3 digits denoting the centre number and the remaining 3 the participant number from 001 to 999. The trial number will be recorded on the screening log.

The eligibility checklist will be completed.

Consent from eligible patients will be sought using the participant information sheet and consent form.

When the consented participant's platelet count falls to $\leq 50 \times 10^9/L$, the PI or delegate will access the on-line randomisation system to randomise the participant (see section 5.5 for further details.)

5. Randomisation

5.1. Allocation – sequence generation

See Section 11.1

5.2. Allocation – concealment mechanism

Participants will be randomised using an online randomisation service (*SealedEnvelope*). Following confirmation of site number and eligibility criteria, a randomisation number will be issued by the system.

5.3. Allocation – implementation

An unblinded NHSBT statistician, independent of the trial team, will generate the randomisation list in accordance with the protocol. A site specific list of coded treatment allocations will also be provided to the trial pharmacist at each site by the same independent NHSBT statistician to enable the pharmacist to dispense the correct trial treatment. Supplies of active and placebo trial treatment will be provided to the hospital pharmacies, labelled with a code so the pharmacist does not know which is active and which placebo.

5.4. Stratification and Randomisation

Participants will be randomised to receive tranexamic acid or a matching placebo in a 1:1 ratio, stratified by site. Randomisation will be balanced within blocks of varying undisclosed sizes.

5.5. Randomisation Practicalities

There will be no exception to eligibility requirements at the time of randomisation.

Eligibility for randomisation will be assessed with reference to the specific inclusion and exclusion criteria.

When a consented participant's platelet count falls to $\leq 50 \times 10^9/L$, the PI or delegate will complete the trial registration/randomisation form and access the web based randomisation

service to randomise the participant. If a patient's platelet count is $\leq 50 \times 10^9/L$ on admission to hospital because they have a newly diagnosed haematological malignancy or refractory disease the patient should be approached for randomisation as soon as possible.

Following randomisation, the randomisation service will e-mail confirmation of the randomisation number to the PI and Trial Manager.

The local PI/delegate is responsible for informing the participant's consultant/physician of the patient's participation in the trial, and for placing a label indicating trial participation on the cover of the patient's medical notes.

The PI/delegate will be responsible for immediately telephoning the pharmacy and speaking with the trials pharmacist, informing them of a patient's participation in the trial and their trial number. A written prescription for trial medication will then be sent to the pharmacy, along with written confirmation of the randomisation number (for example the print-out from the randomisation system). These documents must be received by the clinical trials pharmacist before trial medication may be dispensed.

The trial treatment will be dispensed to the ward to be stored appropriately. Note: the trial treatment shall be commenced as soon as possible within 24, and not later than 72 hours of the first recorded platelet count of $\leq 30 \times 10^9/L$. If a patient's platelet count is $\leq 30 \times 10^9/L$ on admission to hospital because they have a newly diagnosed haematological malignancy or refractory disease the patient should be approached for randomisation and commenced on trial treatment within 24, and not later than 72 hours of starting intensive chemotherapy treatment or conditioning for stem cell transplant.

The PI/delegate must update the centre's screening log by remembering to add trial numbers for all patients randomised.

RANDOMISATIONS
To randomise, please visit

www.sealedenvelope.com

choose the TREATT trial from the drop down list and log-on as instructed

If difficulties are experienced using the randomisation website, then please contact the Trial Manager, who will be able to randomise the patient on your behalf.

5.6. Randomisation Codes

The randomisation service will send confirmation to the PI of the randomisation number and inform the Trial Manager.

5.7. Co-enrolment Guidelines

Participants should not be enrolled in other trials involving platelet transfusions, anti-fibrinolytics, platelet growth factors or other pro-coagulant agents. Co-enrolment in any other trial will be dependent upon the rules stipulated in that trial protocol, and should be discussed with the CI for the other trial.

5.8. Blinding

In this trial, the participants, the PI, the ward nurses, ward pharmacist, all other site staff, and all members of the TMG will be blinded to treatment allocation. The clinical trial pharmacists at each centre will be semi-blinded, in that they will know which participants are in each group, but not what the group is.

5.9. Unblinding

In general, there should be no need to unblind the allocated treatment. Unblinding should be done only in those rare cases when the clinician believes that clinical management depends importantly upon knowledge of whether the participant is receiving TXA or placebo. In those few cases when urgent unblinding is considered necessary, the PI will be given access to the web-based service (www.sealedenvelope.com). Details of this shall be in the Site File. The person performing the unblinding will be sent an e-mail detailing a participant's treatment allocation. The NHSBT 24-hour telephone number is also available: [name]; this will enable the investigator to contact the CI out of hours.

6. Treatment of Participants

6.1. Introduction

This trial has an intervention arm and a control arm. These are described in the sections below.

Trial treatment will be started as per randomisation assignment as soon as possible within 24 hours, and no later than 72 hours, of the first recorded platelet count $\leq 30 \times 10^9/L$, or if the participant was admitted with a platelet count already below $30 \times 10^9/L$ as soon as possible within 24 hours, and no later than 72 hours, after the start of chemotherapy or conditioning for a stem cell transplant

The participant's eligibility criteria MUST be rechecked to ensure they are still eligible prior to first administration of the trial treatment.

The period of time between randomisation and initiation of the trial treatment will allow time for pharmacy to prepare and dispense the trial treatment.

During their inpatient stay haematology patients may experience severe nausea and vomiting, diarrhoea, or significant mucositis. This may impair their ability to tolerate or absorb an orally administered medication. Therefore the trial treatment will initially be given by intravenous administration until the participant is well and able to tolerate the oral medication. The treating physician can then switch the medication to its oral formulation. The date on which the participant is switched from IV to oral formulation will be documented. The participant must receive at least one dose of the IV formulation before transferring to oral. Participants can return to IV after commencing oral IMP, this must be documented, but care must be taken to ensure the correct dose is prescribed.

If the participant has not met the stopping criteria when they are ready for discharge oral IMP should be prescribed.

In other patient groups the dose of tranexamic acid is the same whether it is given therapeutically or prophylactically. Due to differences in bioavailability 1g IV is equivalent to 1.5g PO. This dose is similar to the doses given in the three previous RCTs that have been performed (See Investigator Brochure for further information).

6.2. Interventions

6.2.1. CTIMP to be studied

Tranexamic acid (TXA).

Dose schedule TXA 1g every eight hours IV or 1.5g every eight hours PO.

Comparator or placebo

Placebo (saline) if administration is IV.

Placebo capsule or tablet matched for appearance to TXA if oral.

6.2.2. Description of Trial Drug

Tranexamic acid (Cyklokapron) is trans-4-(aminomethyl)cyclohexanecarboxylic acid, which acts as an inhibitor of fibrinolysis. At the dose used in this study it is a competitive inhibitor of plasminogen activation. Each 10mL vial contains 1g of tranexamic acid (100mg/mL) as an aqueous solution. Vials should be stored between 15° to 25°C. Do not Freeze. Tranexamic acid Injection is administered by infusion, utilising the usual compatible intravenous vehicles (e.g., Sterile Water for Injection, Sodium Chloride for Injection, 5% Dextrose or Ringer's Injection), or slow IV bolus. Parenteral drug products should be inspected visually for particulate matter and discoloration prior to administration, whenever solution and container permit.

The oral preparation will consist of identical tablets from July 2018 (further details available in the Investigator Brochure).

These will be supplied to the clinical trials pharmacist in containers, from which the pharmacist will dispense the required number (according to the randomisation schedule) for the participant.

6.2.3. Blinding of Trial treatment

For intravenous treatment the local investigational drug pharmacy will receive boxes of nine glass vials containing either active drug or placebo. Each box will have a tear off label indicating A or B. Thus, the clinical trials pharmacist will be aware that the participant is receiving treatment A or treatment B; the clinical staff, ward pharmacist and participant will be unaware of the randomisation, as the tear off portion of the label will be removed before dispensing. When a subject is randomised to the trial, the randomiser will receive a randomisation number for the participant and will send confirmation of this, along with a prescription for trial treatment to the clinical trials pharmacist. The clinical trials pharmacist will consult the randomisation list supplied and dispense the trial treatment allocated to the randomisation number.

Labelling of the trial treatment has been changed from Tranexamic acid/placebo to TREATT Trial IMP to prevent inadvertent use of local pharmacy stock TXA.

6.2.4. Administration of Trial treatment

The trial treatment will be started as per randomisation assignment as soon as possible, ideally within 24 hours, and no later than 72 hours, of the first recorded platelet count $\leq 30 \times 10^9/L$. Or, if a patient's platelet count is $\leq 30 \times 10^9/L$ on admission to hospital because they have a newly diagnosed haematological malignancy or refractory disease the patient should be approached for randomisation and commenced on trial treatment within 24 hours,

and no later than 72 hours, of starting intensive chemotherapy treatment or conditioning for a stem cell transplant.

The IV preparation of trial treatment will be administered as a slow IV bolus over 10 minutes every eight hours.

The IV preparation may also be given as an infusion and centres are advised to follow local pharmacy practice for TXA.

IV Tranexamic acid / placebo may be mixed with most solutions for infusion such as electrolyte solutions, carbohydrate solutions, amino acid solutions and dextran solutions.

The IV trial treatment must not be mixed with blood.

The IV trial treatment must not be mixed with solutions containing penicillin.

Three tablets of the oral preparation must be taken with water every eight hours.

6.2.5. Dose Adjustment of Trial treatment in Renal Insufficiency

Renal impairment

In renal insufficiency leading to a risk of accumulation, the use of tranexamic acid is contraindicated in patients with severe renal impairment. For patients with mild to moderate renal impairment, the dosage of tranexamic acid should be reduced according to the serum creatinine level:

Serum creatinine		Dose IV	Dose PO	Administration
µmol/l	mg/10 ml			
120 to 249	1.35 to 2.82	10 mg/kg BW	15 mg/kg BW	Every 12 hours
250 to 500	2.82 to 5.65	10 mg/kg BW	15 mg/kg BW	Every 24 hours
> 500	> 5.65	5 mg/kg BW	Omit dose	Every 24 hours

Oral suggested doses	If creatinine 120 to 249	If creatinine 250 to 500
Participants < 50 kg	500mg BD	500mg OD
Participants 50 to 83 kg	1g BD	1g OD
Participants 84 to 116 kg	1.5g BD	1.5g OD
Participants > 117 kg	2g BD	2g OD

Hepatic impairment

No dose adjustment is required in patients with hepatic impairment.

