6.2.6. Discontinuation of Trial treatment

The trial treatment will be permanently discontinued as soon as any one of the following situations occurs:

1. It has been 30 days since the participant first started the randomised trial treatment.
2. The participant has a spontaneous increase in platelet count from $<30 \times 10^9/L$ to $>50 \times 10^9/L$.
3. The participant has had 3 consecutive days with morning platelet counts $>30 \times 10^9/L$, and no requirement for platelet or granulocyte transfusion, or stem cell transplant.
4. The participant receives open label tranexamic acid, other antifibrinolytic agent or procoagulant drug, (e.g., DDAVP, recombinant Factor VIIa, or Prothrombin Complex Concentrates). Use of these agents will be recorded in trial data.
5. The participant begins anticoagulant or antiplatelet therapy.
6. The participant has visible haematuria.
7. The participant has a diagnosis of thrombosis.
8. The participant becomes anuric (defined as urine output $<10 \text{mls/hr}$ over 24 hours).
9. The participant develops sinusoidal obstructive syndrome (SOS, Veno-occlusive Disease, VOD)

Note: If the trial treatment is discontinued it must not be restarted while the participant remains in the trial.

In addition to the reasons stated above participants may stop treatment early or be stopped early for any of the following reasons:

- Disease progression.
- Unacceptable adverse reaction
- Any change in the participant's condition that justifies the discontinuation of treatment in the opinion of the clinician.
- Withdrawal of consent.

In consenting to the trial, participants are consenting to the trial treatment, trial follow up and data collection. As the participant's participation in the trial is entirely voluntary they may choose to discontinue the trial treatment at any time without penalty or loss of benefits to which they are otherwise entitled. Although the participant is not required to give a reason for discontinuing their trial treatment, a reasonable effort should be made to establish this reason whilst fully respecting the participant's rights.

Participants will remain in the trial for the purpose of follow up and data analysis, unless they withdraw their consent from all stages of the trial, in which case, they should be withdrawn. Data collected up until the time of withdrawal will be retained and included in the analysis.

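### Protocol 6.2.5 contraindicates tranexamic acid in severe renal impairment, yet its table gives an IV dose above 500 µmol/l creatinine, and once treatment has started only anuria forces a renal stop

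*Protocol*

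**What the plan says.** Protocol 6.2.5 gives accumulation as the reason that "the use of tranexamic acid is contraindicated in patients with severe renal impairment". It then introduces its table: "For patients with mild to moderate renal impairment, the dosage of tranexamic acid should be reduced according to the serum creatinine level". The table has three creatinine bands:

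| Creatinine (µmol/l) | IV | Oral |
|---|---|---|
| 120 to 249 | 10 mg/kg every 12 hours | 15 mg/kg every 12 hours |
| 250 to 500 | 10 mg/kg every 24 hours | 15 mg/kg every 24 hours |
| above 500 | 5 mg/kg every 24 hours | omitted |

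The only definition of severe is in Protocol 4.2, which excludes "Patients with severe renal impairment", set at eGFR of 30 ml/min/1.73m² or less. Protocol 6.1 repeats the check once: "eligibility criteria MUST be rechecked to ensure they are still eligible prior to first administration of the trial treatment".

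After that, Protocol 6.2.6 lists nine mandatory stops. The one that concerns renal function is "The participant becomes anuric", meaning under 10 ml/hr over 24 hours. A clinician may also stop for a change in condition that "justifies the discontinuation of treatment in the opinion of the clinician". A note adds: "If the trial treatment is discontinued it must not be restarted while the participant remains in the trial".

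Protocol 8.4 has creatinine measured on days 1 and 2 and then three times a week, or as standard of care, during treatment. No value is tied to stopping.

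**The concern.** One section contains a contraindication, a scope limited to mild to moderate impairment, and a row that doses participants well outside that scope. At entry there is no difficulty, because the eGFR limit and the recheck settle it. Once treatment has begun, neither applies, and a participant above 500 µmol/l who still passes urine meets no mandatory renal stop. The text does not say whether the contraindication or the table then governs.

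One site may follow the row and dose. Another may read the contraindication and stop, and under the 6.2.6 note a stop is permanent even if renal function recovers. What is at stake is participant safety, given the accumulation that 6.2.5 itself cites, and uniform handling across sites. There is a minor effect on the per-protocol set, which depends on the correct dose having been given and on no treatment after a required stop (Protocol 11.4, SAP 4.2.1).

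**Working it through.** **1. The table's cut-points.** Converting with µmol/l × 113.12 / 10,000 = mg per 100 ml:
- 120 gives 1.357 (stated 1.35)
- 250 gives 2.828 (stated 2.82)
- 500 gives 5.656 (stated 5.65)

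The stated values are reproduced to within 0.6%, so the last row does begin at about 5.65 mg per 100 ml. (The second unit column is headed per 10 ml; the figures fit per 100 ml. This is a side matter.)

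**2. Where 500 µmol/l falls against the limit of 30.** The protocol names no eGFR equation, so two standard ones are assumed, with S = creatinine / 88.4 = 500 / 88.4 = 5.656:
- CKD-EPI 2021, for S above k: 142 × (S/k)^−1.2 × 0.9938^age, × 1.012 for women; k = 0.9 for men, 0.7 for women.
- Four-variable MDRD: 175 × S^−1.154 × age^−0.203, × 0.742 for women.

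Example, man aged 18, CKD-EPI: 142 × (5.656/0.9)^−1.2 × 0.9938^18 = 14.0.

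| Age | CKD-EPI, men | CKD-EPI, women | MDRD, men | MDRD, women |
|---|---|---|---|---|
| 18 | 14.0 | 10.5 | 13.2 | 9.8 |
| 50 | 11.5 | 8.6 | 10.7 | 7.9 |
| 75 | 9.8 | 7.3 | 9.9 | 7.3 |

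The range is 7.3 to 14.0. Both equations fall as creatinine and age rise, so every adult in the open-ended row lies at or below 14.0, less than half the limit of 30. The row cannot plausibly be mild to moderate.

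**3. The lower bands.** Solving the same equations for eGFR = 30 gives creatinine of 147 to 265 µmol/l, depending on age, sex and equation. Only one of the twelve combinations exceeds 250 (a man aged 18 under CKD-EPI, 265). By the entry definition, therefore, nearly all of the 250 to 500 band and part of the 120 to 249 band are also severe. A correction confined to the last row would leave that conflict in place.

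**4. The dose in dispute.** Full IV dosing is 3 × 1,000 = 3,000 mg a day. Assumed weights are 50 to 90 kg.
- 5 × 50 = 250 mg a day; 250/3,000 = 8.3%
- 5 × 90 = 450 mg a day; 450/3,000 = 15.0%

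Read as applying on treatment, the contraindication would mean 0 mg.

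**5. Who is exposed.** With 308 of 616 allocated to tranexamic acid, about half of any affected participants would be on placebo. The documents give no frequency for creatinine above 500 µmol/l, and none is assumed.

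**The case against.** The strongest reply is that a coherent reading exists: severe impairment bars entry, the creatinine table governs on treatment, and anuria forces the stop. The section is about dose adjustment, and severe is defined only as an entry criterion. This may well be the intent, but the text does not say so, and the table's own scope sentence contradicts it. It does show that a sentence on precedence is needed, and the fix adopts this reading up to 500 µmol/l.

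Second, the revision history (version 1.4) records that the table was aligned with the Investigator Brochure. The Brochure may explain the row and has to be checked before any dose is changed. It was not available here, and 6.2.5 does not send sites to it for this point.

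Third, there are safeguards: the entry exclusion and recheck, regular creatinine, a dose cut of 85% to 92%, clinician discretion in 6.2.6, and freedom to give alternative treatment in 13.3. These reduce the risk but do not decide between the two instructions.

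Fourth, timing. First enrolment in June 2015 plus 4½ years points to about December 2019, and SAP version 1.1 is dated March 2020. Actual recruitment status is not known, so an amendment might reach few participants or none.

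Three stronger readings are tempting and are not supported:
- A reader might infer from the omitted oral dose that the IV entry is a slip, especially as "Participants can return to IV after commencing oral IMP". Other reasons for omitting tablets are possible, so this is conjecture.
- A reader might infer that treatment must stop whenever eGFR falls to 30. The documents attach that limit only to entry and the recheck, and extending it would remove doses that the lower bands deliberately provide.
- A reader might infer that the main result is at risk. Under SAP 4.2.1, participants stay in the mITT analysis in their randomised arm even if they stop treatment early.

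**Conclusion.** The inconsistency is real and should be corrected. A section that contraindicates the drug in severe impairment prescribes 250 to 450 mg a day IV (50 to 90 kg) at creatinine levels that correspond to an eGFR of roughly 7 to 14 or lower, and after the first dose nothing short of anuria requires treatment to stop on renal grounds.

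This is a low-frequency matter of safety and consistency between sites. The primary mITT analysis is unaffected and the effect on the per-protocol set is marginal. The textual conflict needs no calculation. The judgement that the last row is severe rests on the assumed equations, although the gap to 30 is wide under both. Whether the row was intended depends on the Investigator Brochure, so confidence is moderate.

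**What to change.** First check the Investigator Brochure. Then, in one amendment:

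1. Change the IV entry above 500 µmol/l to an instruction not to give trial treatment, matching the oral entry.
2. Define this as a temporary hold, recorded as missed doses and resumable if creatinine falls to 500 µmol/l or below. It is then not a discontinuation, the no-restart note in 6.2.6 is not triggered, and the participant stays in the per-protocol set, since SAP 4.2.1 keeps those who missed a dose.
3. State that the eGFR limit of 30 applies at entry and at the recheck before the first dose, and that the creatinine table governs on treatment up to 500 µmol/l. Replace the sentence limiting the table to mild to moderate impairment, so that the 250 to 500 band no longer conflicts with the contraindication.

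The cost is a formal amendment with ethics and regulatory approval (Protocol 18) and a notice to sites and pharmacies. A few participants would lose a small, already reduced dose. Creatinine is already collected, so no test is added. The SAP treatment summary already counts missed doses, so no new row is needed. Sample size and primary analysis do not change.
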